4.2.2.4 Background Standard of Care Therapy Compliance

As in Study GA30044, all patients will be expected to continue to record their OCS intake using a diary and as instructed by study staff. Patients will record changes in their OCS dose using a paper diary and as instructed by study staff. OCS usage will be recorded in the Corticosteroid Medication eCRF.

4.2.3 Investigational Medicinal Product Accountability

All IMPs required for completion of this study (GDC-0853) will be provided by the Sponsor where required by local health authority regulations. The study site will acknowledge receipt of IMPs using the interactive voice and Web-based response system (IxRS) to confirm the shipment condition and content. Any damaged shipments will be replaced.

IMPs either will be disposed of at the study site according to the study site's institutional standard operating procedure or will be returned to the Sponsor with the appropriate documentation. The site's method of IMP destruction must be agreed to by the Sponsor. The site must obtain written authorization from the Sponsor before any IMP is destroyed, and IMP destruction must be documented on the appropriate form.

Accurate records of all IMPs received at, dispensed from, returned to, and disposed of by the study site should be recorded on the Drug Inventory Log.

4.2.4 Continued Access to GDC-0853

Currently, the Sponsor (Genentech, a member of the Roche Group) does not have any plans to provide Sponsor study drug GDC-0853 or any other study treatments or interventions to patients who have completed Study GA30066. The Sponsor may evaluate whether to continue providing GDC-0853 in accordance with the Roche Global Policy on Continued Access to Investigational Medicinal Product, available at the following Web site:

http://www.roche.com/policy_continued_access_to_investigational_medicines.pdf

4.3 CONCOMITANT THERAPY, PROHIBITED FOOD, AND ADDITIONAL RESTRICTIONS

Concomitant therapy includes any medication (e.g., prescription drugs, over-the-counter drugs, vaccines, herbal or homeopathic remedies, nutritional supplements) used by a patient from 7 days prior to initiation of study drug through 8 weeks after the last dose of study drug. All concomitant medication taken during the study must be documented on the eCRF along with indication, daily dose, and start and stop dates of administration. Adverse events related to the administration of a concomitant medication or the performance of a procedure must also be documented on the appropriate adverse event page of the eCRF.

It is recommended that patients avoid changing other prescription or non-prescription drugs, vitamins, and dietary supplements within 7 days or 5 half-lives, whichever is longer, prior to the first dose of study medication and throughout the study.

4.3.1 Permitted Therapy

Concomitant immunosuppressant and antimalarial medications can be used up to the doses shown in [Table 2](#).

Table 2 Permitted Dose Ranges for Immunosuppressant and Antimalarial Medications

Azathioprine	Up to 2.5 mg/kg/day
Methotrexate	Up to 25 mg/week
Mycophenolate mofetil	Up to 2500 mg/day
Mycophenolic sodium	Up to 1800 mg/day
Hydroxychloroquine	Up to 400 mg/day
Chloroquine	Up to 250 mg/day
Quinacrine	Up to 200 mg/day
Other	—

Note: Other medications may be permitted (in consultation with the Medical Monitor).

Addition, discontinuation, and dose adjustment of concomitant medications for conditions other than SLE are discouraged but permitted when required for the safe and effective treatment of patients.

Any case of medication intolerance or toxicity must be recorded as an adverse event and any dose modification recorded in the eCRF.

Certain combinations of the SLE therapies below are not permitted (see Section [4.3.2](#))

4.3.1.1 Antimalarials

Antimalarial medications (e.g., hydroxychloroquine, chloroquine, quinacrine), including combinations of up to two antimalarials, are permitted. Replacement of one antimalarial with another may be allowed in cases where there is limited supply of the original medication or if there are issues with toxicity or intolerance.

4.3.1.2 Mycophenolate Mofetil/Mycophenolic Acid

Patients who are taking mycophenolate mofetil (or mycophenolic acid) at permitted doses (see [Table 2](#)) will be eligible to participate in the OLE. When mycophenolic acid is used instead of mycophenolate mofetil, a 360-mg dose of mycophenolic acid is considered to be equivalent to a 500-mg dose of mycophenolate mofetil.

Mycophenolate mofetil may interact with oral contraceptives, decreasing their effectiveness; however, patients enrolling in this study and using hormonal contraceptives as a method of contraception are required to also use a barrier, such as a male condom.

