4.1.1 Inclusion Criteria

Patients must meet the following criteria for study entry:

- Signed Informed Consent Form (see Section 4.4.1)
- Age 18–76 years, inclusive, at time of signing Informed Consent Form
- Able to comply with the study protocol, in the investigator's judgment
- Completion of Study GA30044 up to 48 weeks
- Acceptable safety and tolerability during Study GA30044 as determined by the investigator
- Women of childbearing potential must have a negative urine pregnancy test at baseline

A serum pregnancy test is needed on Day 1 only if the urine pregnancy test is positive.

- For women of childbearing potential (including those who have had a tubal ligation): Agreement to remain abstinent (refrain from heterosexual intercourse) or use a contraceptive method with a failure rate of < 1% per year during the treatment period and for at least 60 days after the last dose of study drug.

A woman is considered to be of childbearing potential if she is postmenarcheal, has not reached a postmenopausal state (≥ 12 continuous months of amenorrhea with no identified cause other than menopause), and has not undergone surgical sterilization (removal of ovaries and/or uterus).

Examples of contraceptive methods with a failure rate of < 1% per year include bilateral tubal ligation, male sterilization, established proper use of hormonal contraceptives that inhibit ovulation, hormone-releasing intrauterine devices, and copper intrauterine devices. Women using estrogen-containing hormonal contraceptives as a method of contraception must also use a barrier, such as a male condom, in conjunction with the hormonal contraceptives.

The reliability of sexual abstinence should be evaluated in relation to the duration of the clinical trial and the preferred and usual lifestyle of the patient. Periodic abstinence (e.g., calendar, ovulation, symptothermal, or postovulation methods) and withdrawal are not acceptable methods of contraception.

- For men: agreement to remain abstinent (refrain from heterosexual intercourse) or use contraceptive measures, and agreement to refrain from donating sperm, as defined below (also see [Appendix 5](#))

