4.2.2.3 Background Standard of Care Therapy

4.2.2.3.1 Immunosuppressant Therapy

Patients should be encouraged to remain stable on their background therapies (e.g., antimalarials, immunosuppressants), but they will be allowed to change doses, discontinue, and/or switch to other permitted immunosuppressant therapies during the

OLE if clinically indicated (see Section 4.3.1). Certain doses and combinations of immunosuppressants are not allowed with GDC-0853 (see Section 4.3.2).

If dose modification (increase or decrease) of an immunosuppressant is required because of increased clinical disease activity or toxicity, this must be recorded as an adverse event on the Adverse Event eCRF, and the dose modification must be recorded in the Immunosuppressant Review eCRF.

Any overdose or incorrect administration of an immunosuppressant should be noted on the Immunosuppressant Review eCRF. Adverse events associated with an overdose or incorrect administration of an immunosuppressant should be recorded on the Adverse Event eCRF.

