Female patients of reproductive or childbearing potential who are unwilling to use a method of contraception that results in a failure rate of < 1 % per year or remain abstinent (refrain from heterosexual intercourse) during the treatment period and for at least 60 days after the last dose of study drug, or longer as required by local requirements for other standard of care medications, will be excluded from study participation.

Abstinence is acceptable only if it is in line with the preferred and usual lifestyle of the patient. Periodic abstinence (e.g., calendar, ovulation, symptothermal, or post-ovulation methods) and withdrawal are not acceptable methods of contraception.

Examples of contraceptive methods with a failure rate of < 1% per year include the following:

- Sterilization, bilateral surgical tubal ligation
- Intrauterine device
- Combined oral contraceptive pill*
- Contraceptive transdermal patch (estrogen and progestin containing)*
- Hormonal vaginal device
- Progestogen-only hormonal contraception associated with inhibition of ovulation
- Implants for contraception
- Injections for contraception (with prolonged release)

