Appendix 5 Childbearing Potential, Pregnancy Testing, and Contraception (cont.)

- Sole sexual partner consisting of surgically sterilized male partner with appropriate postsurgical verification of the absence of spermatozoa in the ejaculate. Patients may provide verbal confirmation that the partner completed appropriate follow-up after vasectomy. Sites are not required to obtain partner medical records.
- Same sex partner
- * **Women using estrogen containing hormonal contraceptives as a method of contraception must also use a barrier such as a male condom in conjunction with the hormonal contraceptives.**

For Men

All men must agree to remain abstinent (refrain from heterosexual intercourse) or use contraceptive measures and agreement to refrain from donating sperm, as defined below:

- With female partners of childbearing potential (including those who have had a tubal ligation), men must remain abstinent or use a condom plus an additional contraceptive method that together result in a failure rate of < 1% per year during the treatment period and for at least 120 days (4 months) after the last dose of study treatment. Men must refrain from donating sperm during this same period.
- With pregnant female partners, men must remain abstinent or use a condom during the treatment period and for at least 28 days after the last dose of study treatment to avoid exposing the embryo.

For Men and Women

[figure not shown]
The reliability of sexual abstinence should be evaluated in relation to the duration of the clinical trial and the preferred and usual lifestyle of the patient. Periodic abstinence (e.g., calendar, ovulation, symptothermal, and post-ovulation methods) and withdrawal are not acceptable methods of contraception.

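### Section 4.3.1.2 offsets the mycophenolate interaction with a barrier for all hormonal-contraceptive users, but the synopsis, Section 4.1.1 and Appendix 5 require a barrier only with estrogen-containing methods

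*Combined protocol and SAP*

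**What the plan says.** Section 4.3.1.2 makes patients on permitted doses of mycophenolate eligible and then raises an interaction: "Mycophenolate mofetil may interact with oral contraceptives, decreasing their effectiveness". It meets that risk by saying that patients enrolling in the study and "using hormonal contraceptives as a method of contraception are required to also use a barrier". The sentence mentions neither estrogen nor mycophenolate, so on its face it covers every user of a hormonal method.

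The inclusion criterion for women in Section 4.1.1, repeated in the synopsis, is narrower: "Women using estrogen-containing hormonal contraceptives as a method of contraception must also use a barrier, such as a male condom". The same criterion gives "established proper use of hormonal contraceptives that inhibit ovulation" as an example of a qualifying method.

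The Appendix 5 footnote is also limited to estrogen: "Women using estrogen containing hormonal contraceptives as a method of contraception must also use a barrier such as a male condom". The asterisk leading to it stands only on the combined pill and the estrogen/progestin patch. The entry "Progestogen-only hormonal contraception associated with inhibition of ovulation" has no asterisk, and neither do implants, injections or the hormonal vaginal device. Appendix 5 does allow for other standard-of-care drugs, but only in how long contraception must last: "or longer as required by local requirements for other standard of care medications".

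Mycophenolate need not be present at entry. Section 4.2.2.3.1 says of patients that "they will be allowed to change doses, discontinue, and/or switch to other permitted immunosuppressant therapies", and Section 4.2.2.3.4 allows a new immunosuppressant as escape therapy. Both sections send the reader to Section 4.3.1. Neither mentions contraception.

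**The concern.** Section 4.3.1.2 names a way in which a permitted background drug could make contraception less reliable, and it offers one safeguard. It words that safeguard as something study patients already have to do. The texts that set the contraception rule for women contain no requirement of that width. The women's criterion in Section 4.1.1 has no cross-reference to Section 4.3.1.2, or to Appendix 5, although the men's criterion does cite Appendix 5. Two sites reading different parts of the protocol could therefore apply different rules to the same woman.

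What is at stake is fetal exposure. Section 1.3.1 reports malformations with GDC-0853 in rats and rabbits, and for that reason makes highly effective contraception a condition of taking part. Section 1.1 notes that lupus occurs mainly in women of childbearing age. Pregnancy tests every 4 weeks through Week 48, and withholding drug after a positive test, shorten exposure once conception has happened. They do not prevent conception.

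**Working it through.** No arithmetic applies. The check sets every barrier statement for women side by side and then runs typical cases through them.

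| Place | Who must add a barrier |
|---|---|
| Section 4.3.1.2 | Users of any hormonal contraceptive |
| Synopsis, inclusion criteria | Users of estrogen-containing methods |
| Section 4.1.1 | Users of estrogen-containing methods |
| Appendix 5, footnote | Users of estrogen-containing methods |
| Appendix 5, asterisks | Combined pill and estrogen/progestin patch |
| Section 4.3.2.2 (CYP3A) | Users of ethinylestradiol-containing products |

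Section 4.3.1.2 is the only place with the wider scope.

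Four women of childbearing potential show where the rules diverge:

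1. *Mycophenolate and a combined pill.* A barrier is required everywhere. There is no gap.
2. *Mycophenolate and an ovulation-inhibiting progestogen-only pill.* Section 4.3.1.2 requires a barrier. Section 4.1.1 and Appendix 5 do not ask for one. This is an oral method, so it falls squarely under the interaction that Section 4.3.1.2 describes. It is the case that matters.
3. *Mycophenolate and a non-oral method without estrogen, such as an implant or injection.* The rules differ as in case 2, but the protocol states the interaction for oral contraceptives only. The wording conflicts, yet the protocol gives no reason to expect reduced effectiveness.
4. *No mycophenolate and a progestogen-only method.* The rules still differ, because the sentence in Section 4.3.1.2 is not confined to mycophenolate users. No interaction is at issue, so this is an inconsistency of text only.

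Case 4 affects the remedy. A new sentence about mycophenolate users alone would leave Section 4.3.1.2 in conflict with the other three places for everyone else on a non-estrogen hormonal method.

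The conflict does not depend on how Section 4.3.1.2 came to be worded. If it was meant to restate the study rule and lost the estrogen qualifier, then the safeguard it relies on does not reach case 2. If it was meant to create a wider rule, that rule is missing from the eligibility criteria and from the contraception appendix.

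**The case against.** The strongest reply is that the scopes differ without contradicting each other. Section 4.1.1 and Appendix 5 never say that users of non-estrogen methods may go without a barrier; they are silent. Section 4.3.1.2 is mandatory in its wording, and a site that follows it satisfies every other section too. It also serves as eligibility text for this group, since it is where patients on mycophenolate are said to be eligible and where they are sent to the dose limits in Table 2. The list of methods gives examples under a performance standard, an annual failure rate below 1%, so an investigator who knows of the interaction should ask whether a pill alone still meets it. Both routes to starting mycophenolate on study lead to Section 4.3.1, and escape therapy also requires that the Medical Monitor be informed.

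Most of this stands, and it sets the priority low. A reader might infer that women on mycophenolate have no barrier safeguard, or that sites will enrol them without one. The documents support neither inference: the requirement is written in the mycophenolate section, and the most that can be said is that a site could miss it.

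The reply does not remove the inconsistency. A woman in case 2 can be checked line by line against Section 4.1.1 and Appendix 5 and pass, with nothing there pointing to the extra requirement. The pointers from the switch and escape sections go to Section 4.3.1 as a whole, for permitted drugs and doses, and do not signal that contraception needs review.

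**Conclusion.** The inconsistency is real and small. One section states a wider barrier rule and relies on it to offset an interaction the protocol itself raises; the synopsis, Section 4.1.1 and Appendix 5 state a narrower one. The practical gap is essentially women of childbearing potential who take mycophenolate with a progestogen-only pill, at a site that works from Section 4.1.1 or Appendix 5 and overlooks Section 4.3.1.2.

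The number of such women cannot be given, because the documents report neither mycophenolate use nor contraceptive methods. No added pregnancy risk can be estimated either, since the protocol says only that effectiveness may fall. A reader might also infer a threat to the trial's results. There is none: no endpoint, analysis population or efficacy summary depends on this text.

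The conclusion takes the interaction as Section 4.3.1.2 states it, for oral contraceptives, and assumes that the sponsor intends the safeguard to apply. It is a low-priority safety harmonisation, worth making because the safeguard is one the sponsor already cites.

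**What to change.** Use one rule in all four places. In the synopsis, Section 4.1.1 and Appendix 5, replace the barrier sentence with wording to this effect:

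> A barrier, for example a male condom, is needed in addition by (a) any woman whose hormonal contraceptive contains estrogen, and (b) any woman taking mycophenolate mofetil or mycophenolic acid, whether at entry or begun during the study, whose contraceptive is an oral hormonal product of any kind, including a progestogen-only pill.

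Mark the progestogen-only entry in Appendix 5, noting that the mark applies to oral products taken with mycophenolate. Reword Section 4.3.1.2 to state the same rule and to cross-reference Section 4.1.1 and Appendix 5.

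This option narrows what Section 4.3.1.2 now says about non-oral methods without estrogen, and about women not on mycophenolate, so the sponsor should confirm that this is intended. If the all-hormonal scope is intended, keep Section 4.3.1.2 as it is, delete the estrogen limit in the other three places, and mark every hormonal entry in Appendix 5.

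The cost is a sentence in three places, a reworded sentence in Section 4.3.1.2 and a mark in Appendix 5, which can go into an amendment. Under the first option the added burden falls on a few women, for whom Section 4.3.1.2 already states the barrier. The second option reaches every woman on a non-estrogen hormonal method and so asks somewhat more.

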4.3.1.3 Azathioprine

Prior to starting azathioprine, it is strongly recommended to test patients for thiopurine methyltransferase variant alleles that have been associated with decreased activity in vitro and lead to the accumulation of the drug and/or its metabolites.

4.3.1.4 Methotrexate

To prevent methotrexate-associated adverse events, all patients on methotrexate are required to take folic acid or equivalent (e.g., 1 mg/day) at a stable dose of at least 5 mg/week or equivalent.

4.3.1.5 Non-Steroidal Anti-inflammatory Drugs

As needed use of NSAIDs should be avoided within 24 hours before a visit where clinical efficacy assessments are scheduled to be performed and recorded.

Aspirin can be taken to reduce cardiovascular risk, but the dose is not to exceed 325 mg/day.

In order to prevent NSAID-related GI complications in high-risk patients, concomitant acid reducing agents (e.g., PPIs) should be used according to local guidelines (see [Section 5.1.1.3](#)).

4.3.1.6 ACE Inhibitors and ARBs

For patients who are on angiotensin converting enzyme (ACE) inhibitors or angiotensin receptor blockers (ARBs) at study entry, doses of ACE inhibitors or ARBs should be kept stable throughout the first half of the trial whenever possible.

4.3.1.7 Dietary Supplements

For the purposes of this protocol, dietary supplements are defined as vitamins, minerals, purified food substances, and herbals with pharmaceutical properties. Vitamins,

minerals, and purified food substances are allowed in amounts not known to be associated with adverse events (e.g., hypervitaminosis). Herbals with pharmaceutical properties are allowed only if there is acceptable evidence of no CYP3A inhibition or induction (refer to [Appendix 7](#) for a list of prohibited concomitant medications, including herbal products, as well as Section [4.3.2.2](#)). Otherwise, herbals with pharmaceutical properties must be discontinued for at least 4 weeks prior to the first dose of study medication, unless there is sufficient data available regarding the duration of an herbal medication's PK and PD effects to allow a shorter washout to be specified (e.g., 5 half-lives). Please direct any questions to the Medical Monitor.

4.3.1.8 Acid Reducing Agents

Patients who use short-acting antacids (e.g., Maalox[®], Pepto-Bismol[®], Roloids[®] for symptomatic relief of heartburn) should take GDC-0853 or matching placebo 2 hours before or 2 hours after short-acting antacid administration because gastric acid improves GDC-0853 absorption. Patients may be treated with PPIs or H₂RAs at up to the maximum recommended dose according to local labeling. The dose is recommended to remain stable throughout the study. At visits with scheduled PK assessments (see [Appendix 1](#)), any use of PPIs (see Section [4.2.2.1](#)), H₂RA, and/or short-acting antacids should be recorded as concomitant medications, including the date and time of last administration prior to the clinic visit.

4.3.2 Prohibited Therapy

A listing of concomitant medications and foods that are prohibited or should be used with caution due to potential PK drug–drug interactions is provided in [Appendix 7](#). Biologic response modifiers and disease-modifying antirheumatic drugs other than mentioned above are not allowed during this study, and any use will require discontinuation of study treatment.

Specifically, the use of the following therapies is prohibited in conjunction with study drug treatment:

- All biological agents (e.g., tumor necrosis factor inhibitors, IL-17, IL-12/23, abatacept, denosumab) including biosimilars (investigational or approved)
- Anti-CD20 monoclonal antibody
- Belimumab (Benlysta[®])
- Chlorambucil
- Cyclophosphamide
- Heparin, low molecular weight heparin, and other injectable systemic anticoagulants
- Immunosorbent column
- Investigational therapy other than study drug
- Oral anticoagulants, including but not limited to warfarin, dabigatran, rivaroxaban, and apixaban

- Sirolimus
- Systemic calcineurin inhibitors (e.g., tacrolimus, cyclosporine)
- Tocilizumab and other anti-IL6R or anti-IL6 agents
- Tofacitinib and other JAK inhibitors
- Any combination of azathioprine, methotrexate, mycophenolate mofetil, or mycophenolic sodium

Please see [Appendix 7](#) for additional prohibited therapies during this study.

